5.6. Measurements of Treatment Compliance

Percent compliance by dose regimen and dose frequency (360 mg daily, 1080 twice weekly, and/or 1080 mg every 3 days) will be calculated for Part B and Part A + B, by disease group using the Safety Population as follows:

 $Part A Compliance (\%) = \frac{administered during Part A}{total number of expected study doses during Part A} \times 100$

Unless otherwise noted, during the Part A, the number of expected doses is the number of days during Part A for subjects that did not roll over into Part B. For subjects that rolled over into Part B, the expected number of doses is the number of days during Part A minus 1 to account for the skipped dose prior to the dose transition.

number of completed study dosesPart B Compliance (%) = $\frac{administered during Part B}{total number of expected study doses during Part B} \times 100$

That is, when subjects receive twice weekly dosage, percentage compliance will be calculated as:

 $actual number of completed study doses \\ Compliance (\%) = \frac{administered}{(last dose date - first dose date + 3.5)/7) \times 2} \times 100$

When subjects receive every 3 days dosage, percentage compliance will be calculated as:

 $\begin{array}{l} \mbox{actual number of completed study doses} \\ \mbox{Compliance (\%)} = & \frac{administered}{(last \ dose \ date - first \ dose \ date)/3 + 1} \times 100 \\ \end{array}$

Part A + B compliance will be calculated as:

```
Part A + B Compliance (%)

number of completed study doses

= administered during Part A + number of completed study doses

administered during Part B

total number of expected study + total bumber of expected study

doses during Part A doses during Part B
```

If the investigator instructed the subject to stop taking study medication for a period of time, e.g. due to an adverse event, then this period will not be included in the denominator for the compliance calculation.

The number and percentage of subjects who had a percentage of drug compliance range by increment of 10% (<80%, $\ge 80\%$ - <90%, ≥ 90 - $\le 100\%$, and >100%) will then be presented in a table by disease group.

By-subject listings will be produced for treatment compliance and exposure.

5.7. **Protocol Deviations**

All protocol deviations will be reviewed and documented before database lock. Protocol deviations will be recorded by the site staff separately from the clinical database. They may also be identified through programmable checks of the data.

Key protocol deviations include any violations of inclusion and exclusion criteria. This includes unknown violations at enrollment and on-study violations, such as taking a prohibited medication.

The CRO/Apellis will classify major and minor protocol deviations per the agreed protocol deviation management plan. The Apellis study team will review the protocol deviations and their classification throughout the study and before database lock.

Number and percentage of subjects with protocol deviation will be tabulated by importance of deviation for Part B and Part A + B, and by disease group for the Safety Population.

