## **Duration of Study Participation:**

The planned length of participation in the study for each subject is 76 weeks, including an approximate 4-week screening period, 48-week treatment period and 24-week follow-up period (Part A, Core Study Phase). Any subject who, in the opinion of the investigator, is experiencing clinical benefit from pegcetacoplan administration will be invited to participate in Part B, a Long-Term Extension Phase in order to continue to receive treatment with pegcetacoplan until it is commercially available for the disease under treatment. If invited to participate in Part B, the subject can enter the Long-Term Extension Phase as soon as they complete the 48-week treatment period and do not need to participate in the 24-week follow-up period.

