### **10.1.** Transition to Twice-Weekly Dosing

Patients are able, at the discretion of the sponsor, to transition to twice-weekly dosing with 1080 mg pegcetacoplan prior to the Long-Term Extension Phase, but not earlier than Week 24. If a dose transition occurs during Part A, the subject will need to follow the dose transition visits, outlined in Table 2 below. Dose can be adjusted, as needed, to maintain clinical response.

Transition Visits (T1, T2, and T3) should be scheduled for 1, 2, and 4 weeks after the first day on which their dose was adjusted. Additionally, subjects should be instructed to skip their Core Study Phase dose the day before the visit at which their dose will transition.

**Table 2:** Part A, Dose Transition Visits

		Dose Transition Visits	
Study Week	T+1W	T+2W	T+4W
Study Day	T+7D	T+14D	T+28D
Study Visit	T1	T2	Т3
Visit Window (±Days)	2	2	2
Physical examination a			
Triplicate 12-lead electrocardiogram			
Pegcetacoplan administration b	X	X	X
Injection site assessment c	X	X	X
Concomitant medications	X	X	X
Vital sign measurements d	X	X	X
Urinalysis	X	X	X
Return uPCR samples		X	X
Bloode	X	X	X
Pharmacokinetics f	X	X	X
Antidrug Ab assays g			X
Hematology and chemistry	X	X	X
PD for Complement profile f	X	X	X
Pregnancy (β-HCG and FSH)			
Urine pregnancy test h			X
Adverse events	X	X	X
Drug Dispensation for Home Administration	X	X III. in a sign of a	X

Abbreviations:  $\beta$ -HCG = beta human chorionic gonadotropin; ECG = electrocardiogram; IP = investigational product; PD = pharmacodynamic; PI = primary investigator; SC = subcutaneous; uPCR = urine protein-to-creatinine ratio; WOCBP = women of childbearing potential.

- a Symptom-driven physical examinations may be performed at unscheduled time points if deemed necessary by the PI.
- b Subjects will self-administer SC pegcetacoplan, after receiving appropriate training by a research nurse or other personnel. During site visits subject will self-administer pegcetacoplan at the site if the visit occurs on a dosing day. If the visit falls on a nondosing day, no IP administration is needed.
- c Between site visits, subjects will be instructed to report any injection site reaction to the study coordinator.

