### **12.2.2. Dosing**

Starting on Day 1 (Visit 4), subjects will receive self-administered daily SC doses of 360 mg of pegcetacoplan until at least Week 24 (Visit 11) and then as directed based on the timing of transition to twice-weekly dosing, and whether they are following Part A (Follow-up) or Part B (Long-Term Extension). Of important note, patients may be switched over to twice-weekly dosing with 1080 mg, as early as Week 24, but no later than the entrance into the extension phase of the study; timing of the switch is at the discretion of the sponsor. If dose transition occurs, the subject will need to follow the dose transition visits (T1, T2, and T3), as outlined in Section 10.1, Table 2 (Part A) or Appendix 1, Table A1 (Part B). The dose can be adjusted, as needed, to maintain clinical response, but no more than 1080 mg every third day.

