#### A1.1.4.2. Part B Pegcetacoplan Dosing

Starting at Week 48, subjects will receive SC infusions pegcetacoplan at a dosage of 1080 mg twice weekly. During the course of the study, subjects may be switched to an alternate dosing regimen of pegcetacoplan at 1080 mg every 3 days, if warranted, based on clinical response and agreement from the sponsor (see Section A1.1.3.2).

Dosing diaries will be utilized for pegcetacoplan and are to be completed for each dose administered at the study site or outside regular clinic visits. Subjects should not deviate from their pegcetacoplan dosing schedule: Day 1 and Day 4 of each treatment week (eg, Monday/Thursday/Monday) or every 3 days (eg, Monday/Thursday/Sunday).

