For each disease group, patients whose underlying renal disease is stable for at least 2 months prior to the first dose may enter the study. In this trial, stable renal disease should include stable eGFR, proteinuria and blood pressure, as well as a stable and optimized treatment regimen for their renal disease, in the opinion of the PI (See Protocol Section 10.1 for the complete detailed eligibility information). Upon completion of the screening period, patients who meet all of the inclusion and none of the exclusion criteria will begin the treatment phase of the study. The treatment phase will consist of once daily, self-administered, SC dosing of 360 mg APL-2 at home, with the exception of all scheduled clinic visits. During scheduled Visit 4 only, the site staff will assist in administering the first SC dose of APL-2. At Visits 5-15, subjects will self-administer APL-2 in the presence of the site staff and undergo various safety and efficacy assessments by qualified site staff. Subjects may be switched over to twice weekly dosing as early as Week 24. Any subject who is invited to participate in Part B who has not already switched over to twice weekly dosing of 1080 mg, must do so at the beginning of Part B. If a subject transitions to the twice weekly dosing, they need to follow the dose transition visits (T1, T2, and T3) as outlined in Protocol Section 10.1, Table 2 (during Part A) or Protocol Section 18, Table 6 (for Part B). The change in proteinuria from baseline through the end of treatment will be assessed as the primary endpoint. Urinary PCR will be used to measure changes in proteinuria for the primary endpoint.

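### Part A + B compliance is understated for any subject who moved to twice-weekly dosing during Part A, because the Part A denominator assumes one dose per day throughout

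*SAP*

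**What the plan says.** SAP 5.6 calculates compliance for Part B and for Part A + B, by disease group, in the Safety Population. SAP 4.2 limits that population to subjects who rolled over and received at least one 1080 mg dose.

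Two sentences set expected Part A doses. For subjects who did not roll over: "Unless otherwise noted, during the Part A, the number of expected doses is the number of days during Part A". For subjects who did: "the expected number of doses is the number of days during Part A minus 1", the 1 being the dose skipped before the transition. The second sentence therefore governs everyone in the compliance table.

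Twice-weekly and every-3-days formulas follow the Part B formula and are introduced as an elaboration of it. The Part A + B formula adds the Part A and Part B completed doses and divides by the sum of the two expected counts. Results are banded as <80%, 80% to <90%, 90% to 100% and >100%, and listed by subject.

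On timing of the switch, SAP 3.1 says "Subjects may be switched over to twice weekly dosing as early as Week 24", and Protocol 12.2.2 gives the range as "as early as Week 24, but no later than the entrance into the extension phase of the study". SAP 13.4.2 and 13.4.3 contain separate visit-window tables for subjects whose transition visits fell in Part A, so the SAP anticipates such subjects.

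**The concern.** The calendar-day denominator is right only for a subject who stays on daily dosing to the end of Part A. After a switch within Part A the expected count falls from seven doses a week to two, but the denominator keeps counting seven. A subject who takes every assigned dose then appears to have missed many.

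The Part A count feeds the combined formula, so the shortfall reaches the Part A + B table and the by-subject listings. It acts in one direction and only on subjects who switched during Part A. With 6-12 subjects planned per disease, and only those continuing into Part B counted, one subject placed in the wrong band visibly changes a percentage.

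**Working it through.** The plan gives no compliance figure to reproduce, so this is a direct dose count for a subject who misses nothing.

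**Inputs**
- Part A treatment: "48-week treatment period" (Protocol synopsis), with the Week 48 visit on Day 336 (Protocol Table 1). The SAP denominator is 336 − 1 = 335.
- Earliest switch: Week 24, Day 168 (Protocol 12.2.2 and Table 1).
- Skipped dose: "subjects should be instructed to skip their Core Study Phase dose the day before the visit at which their dose will transition" (Protocol 10.1).
- Twice-weekly pattern: "Day 1 and Day 4 of each treatment week" (Protocol A1.1.4.2). This is stated for Part B and assumed here for Part A as well.
- Part B length: open-ended in the protocol, so 24, 48 and 72 weeks are assumptions.

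**Where the rule works.** A subject on daily dosing to the end who transitions at Visit 15 doses on Days 1 to 334 and skips Day 335. With Day 336 counted in Part B, compliance is 334/(335 − 1) = 100%.

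**Switch on Day S within Part A**
- Daily doses are taken on Days 1 to S − 2, so their number is S − 2.
- Day S − 1 is skipped.
- Twice-weekly doses run from Day S to Day 336, with gaps of 3 and 4 days.
- Part A component = (daily + twice-weekly doses) / 335.
- Part A + B with w fully adherent Part B weeks = (Part A doses + 2w) / (335 + 2w).

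For Week 24: 168 − 2 = 166 daily doses and 49 twice-weekly doses, a total of 215, so 215/335 = 64.2%. With w = 48: (215 + 96)/(335 + 96) = 311/431 = 72.2%.

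| Switch | Daily + twice weekly | Part A component | A + B, w = 24 | w = 48 | w = 72 |
|---|---|---|---|---|---|
| Week 24 | 166 + 49 = 215 | 64.2% | 68.7% | 72.2% | 74.9% |
| Week 30 | 208 + 37 = 245 | 73.1% | 76.5% | 79.1% | 81.2% |
| Week 36 | 250 + 25 = 275 | 82.1% | 84.3% | 86.1% | 87.5% |
| Week 42 | 292 + 13 = 305 | 91.0% | 92.2% | 93.0% | 93.7% |

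**Time to leave the <80% band (Week 24 switch).** Solve (215 + x)/(335 + x) = 0.80. Then x = (268 − 215)/0.20 = 265 doses, or 132.5 weeks of perfect Part B dosing.

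**Sensitivity to the Day 336 dose.** If that dose is left out of the numerator, the Part A component is 214/335 = 63.9%, and reaching 80% takes (268 − 214)/0.20 = 270 doses, or 135 weeks. If Part A ends on Day 335, it is 214/334 = 64.1% and 133 weeks. For the Week 24 switch these choices move the percentages by at most about 0.3 point and change no band.

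**After the correction.** Using the twice-weekly denominator already in SAP 5.6, the Week 24 switcher is expected to take 166 + ((336 − 168 + 3.5)/7) × 2 = 166 + 49 = 215 doses, and 215/215 = 100.0%. Switches at Weeks 30, 36 and 42 also return 100.0%.

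**The case against.** The strongest reply is that SAP 5.6 already intends a regimen-specific calculation. Its opening sentence promises compliance by regimen and frequency, the twice-weekly formula is not labelled as Part B only, and SAP 5.5 sums duration by regimen. A careful programmer could put these together. What stands is that the intent is visible; what is missing is the instruction. The opening caveat in "Unless otherwise noted, during the Part A, the number of expected doses is the number of days during Part A" belongs to the sentence on subjects who did not roll over, and no exception for a Part A switch is written anywhere. Naming the regimen supplies no denominator: a daily row computed with the written rule would give the Week 24 switcher 166/335 = 49.6%. The clause removing investigator-instructed interruptions from the denominator does not help either, since a change of frequency is not an interruption.

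Other limits are fair and are accepted:
- Compliance is reported for Part B and Part A + B, so the 64% is a component of a reported figure and not a planned summary in itself.
- The per-protocol definition in SAP 4.3 names no compliance cut-off, and SAP 6 plans no formal inference.
- The by-subject listings and the durations by regimen would help an alert reader spot the artefact.

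A reader might also infer that adherent subjects will be declared non-compliant, or that low adherence will appear tied to the twice-weekly regimen. The documents support neither. The SAP defines bands and no non-compliance label, and the banded table is by disease group and not by switch time.

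**Conclusion.** The Part A denominator in SAP 5.6 is wrong as written for any roll-over subject who changed regimen within Part A, and the error carries into Part A + B compliance. For a fully adherent Week 24 switcher the combined figure is about 69% to 75% over an assumed 24 to 72 weeks of Part B, where it should be 100%. It remains in the <80% band until roughly 132 to 135 weeks. The understatement shrinks with later switches: a Week 36 switch reads about 84% to 87% and a Week 42 switch about 92% to 94%.

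These figures assume that the Part B twice-weekly pattern also applied in Part A and that no dose was missed. The number of Part A switchers is not given, so the effect on the summary table cannot be computed; it is nil if nobody switched early. The consequence is confined to a descriptive compliance table and listings. It would be wrong to infer that efficacy estimates or per-protocol membership are affected by this rule, since neither is tied to a compliance percentage in the SAP.

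**What to change.** In SAP 5.6, define Part A expected doses as the sum over the regimen periods actually assigned:
- days on daily dosing, minus the one skipped day before the transition, counted once in the part where it falls;
- plus scheduled twice-weekly doses from the transition to the end of Part A;
- plus any every-3-days doses in Part A, because the adjustment option in Protocol 12.2.2 is not limited to Part B.

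Use the twice-weekly and every-3-days formulas already in SAP 5.6, state that they apply in either part, and carry the resulting sum into the Part A + B denominator. State also whether the Day 336 dose belongs to Part A or Part B.

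The cost is one or two SAP sentences and a programming change. The start and stop dates of each regimen are needed in any case for the durations by regimen in SAP 5.5. This is an analysis definition only and implies nothing about which regimen is appropriate.

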13. DATA HANDLING CONVENTIONS

13.1. General Data Reporting Conventions

All statistical analyses will be performed using SAS® (Version 9.4 or higher, SAS Institute Inc., Cary, NC, USA).

Categorical variables will be tabulated as number of subjects and percentage of total number of subjects in the given analysis set as noted for each category. Percentages will be reported to one decimal place.

Descriptive statistics will be used to summarize continuous variables including number of subjects, mean, standard deviation (SD), median, minimum and maximum. Mean and median will be reported to 1 more decimal place than the raw data, while the SD will be reported to 2 more decimal places than the raw data. Minimum and maximum will be reported the same as the original data.

In general, all analyses will be performed for Part B and Part A + B unless otherwise specified. Subject specific listings will be provided by disease group, subject ID, Study Part and visit, if applicable.

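### SAP 5.6: the twice-weekly compliance formula places a perfectly adherent subject in the >100% category when the first counted dose is a Day 1 dose and the last is a Day 4 dose

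*SAP*

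**What the plan says.** SAP 5.6 defines compliance as completed doses over expected doses, separately by regimen. It states that "when subjects receive twice weekly dosage, percentage compliance will be calculated as" completed doses over an expected number built from "last dose date - first dose date + 3.5)/7", multiplied by 2. For the other Part B regimen, introduced by "When subjects receive every 3 days dosage, percentage compliance will be calculated as", it is (last − first)/3 + 1. For roll-over subjects in Part A, "the expected number of doses is the number of days during Part A minus 1". The Part A + B figure adds the two numerators and the two denominators.

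Subjects are then grouped as <80%, ≥80 to <90%, ≥90 to ≤100%, "and >100%) will then be presented in a table by disease group". SAP 5.6 does not round the expected count, cap the result or allow a tolerance at 100%. Its only adjustment removes periods when the investigator told the subject to stop. SAP 13.1 adds the general rule "Percentages will be reported to one decimal place".

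The dosing calendar is in protocol A1.1.4.2: "Subjects should not deviate from their pegcetacoplan dosing schedule", which for the twice-weekly regimen is "Day 1 and Day 4 of each treatment week (eg, Monday/Thursday/Monday").

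**The concern.** The 3.5 in the formula is the average gap between doses. On a Day 1/Day 4 calendar no actual gap has that length: each is 3 or 4 days. The average is right over whole weeks only. If the counted period starts on one dose of the week and ends on the other, the expected number is not a whole number and cannot equal the scheduled count.

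The error is a fraction of a dose, but one category boundary lies exactly at 100%, where a perfect complier belongs, so any excess changes the category. Two equally adherent subjects can be tabulated differently because of which dose of the week came last. Groups are small. The protocol plans 6 to 12 patients per disease, so even if all entered Part B, one misplaced subject would move a category by 1/12 = 8 to 1/6 = 17 percentage points. The tables could also disagree with each other. SAP 5.5 counts subjects who took every infusion as prescribed, and the same person could appear there and in the >100% row of SAP 5.6.

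**Working it through.** **Inputs**
- Expected doses, SAP 5.6: ((last − first + 3.5)/7) × 2. The printed brackets are unbalanced, possibly from text extraction; this is the only sensible reading.
- Calendar, protocol A1.1.4.2: Day 1 and Day 4 of each week, with no deviation.
- Categories, SAP 5.6; one-decimal reporting, SAP 13.1.

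The plan gives no numerical compliance result, so there is no figure to reproduce. The formula is applied directly to a subject who misses nothing.

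**First dose Day 1, last dose Day 4, w weeks.** Doses taken = 2w. Span = 7(w − 1) + 3 days. Expected = 2 × (7w − 4 + 3.5)/7 = 2w − 1/7.

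| Weeks | Taken | Expected | Compliance |
|---|---|---|---|
| 1 | 2 | 1.857 | 107.7% |
| 2 | 4 | 3.857 | 103.7% |
| 4 | 8 | 7.857 | 101.8% |
| 12 | 24 | 23.857 | 100.6% |
| 24 | 48 | 47.857 | 100.3% |
| 48 | 96 | 95.857 | 100.1% |

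The excess is always 1/7 of a dose, so the unrounded result is above 100% at every w. One-decimal rounding first gives 100.0% at w = 143 weeks.

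**First and last the same dose of the week** (Day 1 to Day 1, or Day 4 to Day 4). Span = 7k, taken = 2k + 1, expected = 2 × (7k + 3.5)/7 = 2k + 1. Compliance is exactly 100%.

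**First dose Day 4, last dose Day 1, 2w doses.** Span = 7(w − 1) + 4, expected = 2w + 1/7. For 24 doses: 24/24.143 = 99.4%. This is too low, but the subject stays in ≥90 to ≤100%.

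**One missed dose, Day 1 to Day 4.** (2w − 1)/(2w − 1/7) is below 100% for every w. At 24 weeks it is 47/47.857 = 98.2%, against a true 47/48 = 97.9%.

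**Every-3-days formula, for comparison.** n doses span 3(n − 1) days, so expected = n and compliance = 100%. The fault is specific to the twice-weekly formula.

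**Part A + B.** Assume 336 Part A days, daily dosing throughout and 335 of 335 expected doses taken. Compliance = (335 + 2w)/(335 + 2w − 1/7): 359/358.857 = 100.04% at 12 weeks of Part B and 431/430.857 = 100.03% at 48. Unrounded, these exceed 100%; at one decimal they print as 100.0%. The SAP does not say whether subjects are categorised on the rounded or unrounded value.

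**The case against.** The strongest objection concerns scope. A reader might infer that every perfect complier whose last dose is the second of the week exceeds 100%. The documents do not support that, because both ends of the period matter: Day 4 to Day 4 gives exactly 100%. Nor is a Day 1 start assured. It is natural for subjects who begin the regimen at Visit 15 (protocol A1.1.2). Others may have switched from Week 24 onward (protocol 10.1), and Visit 15 has a ±2-day window, so their first Part B dose could be either dose of the week. The Day 1/Day 4 rule itself is stated only for Part B. This objection stands and is built into the point.

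A reader might also infer that these subjects are reported as over-dosed. The SAP labels the category only by its range, and protocol 15.4 defines overdose by dose and frequency and handles it separately. The SAP 5.5 counts of missed and complete infusions, with the by-subject listings, would let a careful reader see that 100.3% is not an extra dose. They lower the risk of misreading but do not correct the category.

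Finally, nothing else depends on the table. The Per Protocol definition in SAP 4.3 has no compliance threshold, and SAP 6 applies no formal inference. That limits the weight of the point, not its correctness.

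**Conclusion.** The point holds as a minor error in a stated rule. For a subject with no missed dose, a Day 1 first counted dose and a Day 4 last dose, the formula gives 101.8% at 4 weeks, falling to 100.1% at 48, and the wrong category. It rests on the Day 1/Day 4 calendar being followed exactly and on the reading of the brackets given above. Misplacement above 100% cannot affect a subject who missed a dose within the counted period, so the formula does not hide poor adherence there. It matters mainly for Part B; for Part A + B it depends on whether rounded values are categorised.

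How many subjects are affected cannot be derived. It is tempting to say about half of perfect compliers who start on Day 1, but that assumes the last dose is equally likely to be either dose of the week. The documents do not say so, and they give no number of subjects without missed doses.

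**What to change.** In SAP 5.6, define expected twice-weekly doses as the number of scheduled Day 1 and Day 4 doses from first to last counted dose, inclusive. Alternatively, round the existing expression to the nearest whole dose before dividing and categorising. Rounding works because 2w − 1/7 and 2w + 1/7 both become 2w, and 2k + 1 is unchanged; either method returns exactly 100.0% for a perfect complier. Use the same count in the Part A + B denominator. The cost is one line in the SAP and one in the program, plus a rerun of the compliance outputs if they already exist. Data collection and patient management are not affected.
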